### **3.10 Study conduct and GCP Compliance Statement**

This study will be conducted in compliance with the protocol approved by the Institutional Review Board (IRB), and according to Good Clinical Practice (GCP) standards. No deviation from the protocol will be implemented without the prior review and approval of the IRB except where it may be necessary to eliminate an immediate hazard to a research patient. In such case, the deviation will be reported to the IRB as soon as possible.

### **3.11 Risks and Benefits**

#### **3.11.1 Potential Risks**

The risks associated with this study can be divided into those related to the intravitreal injection of RST-001, the RST-001 treatment and study procedures.

##### **3.11.1.1 Intravitreal Injection**

These risks are well recognized and include transient conjunctival hyperemia and hemorrhage at the injection site. Serious complications such as retinal tears/holes, retinal detachment, vitreous hemorrhage and endophthalmitis are uncommon or rare but may result in reduced vision and may require surgical intervention.

##### **3.11.1.2 RST-001 Treatment**

The risks of intravitreally-administered RST-001 are not known. Potential risks include an immune response, which may result in ocular inflammation and the associated consequences.

##### **3.11.1.3 Study Procedures**

The risk from the tests performed in this study carry minimal risks and mostly relate to the need for pupillary dilation, which typically results in temporary blurred vision and increased light sensitivity. On occasion, a corneal abrasion can result from the use of the ERG contact lens.

### **3.12 Protection from Risks**

The RST-001 drug product has been manufactured in compliance with current Good Manufacturing Practice (cGMP). Extensive testing has been performed to ensure infective agents and pathogens are not present.

Intravitreal injection of RST-001 will be performed in the operating room under aseptic conditions by qualified staff in accordance with the Study Procedures Manual.

After the procedure, each patient will be carefully monitored for complications. Evidence of an immune response to RST-001 will be monitored (refer to Section 6.2.1).

The conduct of this study will be overseen by the DSMC.

### **3.13 Provisions for Injury**

Any complications arising post injection will be managed in accordance with the investigator's standard of care.

It is not possible for RST-001 to be removed from the eye after injection.

### **3.14 Potential Benefits**

Patients may not benefit directly from the study. It is theoretical at this time as to whether any visual benefit will be afforded by RST-001. The primary objective of this particular study is to establish safety of RST-001.

#### **3.14.1 Risk Benefit Analysis**

Since RST-001 has not yet been shown, in humans, to be efficacious, investigators and patients will need to weigh carefully the risks shown above with the theoretical possibility of improved or preserved visual function.

### **3.15 Study Overview**

#### **3.15.1 Study Design**

This is an open-label, dose-escalation study to evaluate the safety and tolerability of RST-001 administered as a single intravitreal injection in patients with advanced RP.

#### **3.15.1.1 Enrollment Phase 1**

Three groups of patients (A, B, C, each comprising of approximately but no less than three patients) will be enrolled in this study.

Approximately 3 patients in Group A will receive the lowest dose of RST-001 (LOW). The safety and tolerability of RST-001 will be assessed in the first patient for a minimum of one month (to include Month 1 Visit). If the DSMC considers the safety and tolerability of the first patient satisfactory and the enrollment stopping rules have not been met, then the remaining patients in Group A can be enrolled and receive treatment.

If the DSMC considers the safety and tolerability of Group A satisfactory and the enrollment stopping rules have not been met after a minimum assessment of one month (to include Month 1 Visit) from the last treatment group, then approximately 3 patients in Group B may be enrolled and receive a higher dose of RST-001 (MID) following the same guidelines and treatment schedule.

Similarly, if the DSMC considers the safety and tolerability of Group B satisfactory and the enrollment stopping rules have not been met after a minimum assessment of one month (to include Month 1 Visit) from the last treatment group, then approximately 3 patients in Group C may be enrolled and receive the highest dose of RST-001 (HIGH) following the same guidelines and treatment schedule.

[figure not shown]
After completion of the 2-year core study visits, each patient will be enrolled in a long-term follow-up for an additional 3 years to monitor the long-term safety of RST-001.

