#### **3.6.2.1 Dog Study**

The dog study was conducted in healthy male and female animals 5-6 months of age. The dog was chosen as the animal model for this study as it is an accepted non-rodent species for preclinical ocular toxicity testing by regulatory agencies. There were 8 dogs per dose group and 4 dose groups. Actual doses verified were vehicle (control); [REDACTED] (Low), [REDACTED] (Mid), and [REDACTED] (High) vg/eye of RST-001. Two dogs/sex/time point were administered, in the right eye, a single- [REDACTED]  $\mu$ L intravitreal injection of vehicle or RST-001. Animals were sacrificed on Day 36 and Day 99.

No noteworthy adverse effects were observed in the body weight, food consumption, clinical pathology or organ weights following administration of RST-001 at any dose level.

RST-001-related findings, consisting of ocular inflammation, were observed beginning at least 5 weeks after administration with an increasing incidence and severity with dose at all dose levels. Ophthalmic findings of anterior uveitis (anterior chamber cells, keratic precipitates and/or cell-like deposits on the corneal endothelium) were observed at Week 5 in 8/8 high dose eyes and 3/8 or 1/8 eyes for the mid and low doses, respectively. During the recovery period, findings generally remained stable or progressed. Findings related to chronic inflammation, including the presence of perivasculär retinal opacities in addition to findings in the anterior chamber, were present at all dose levels at the end of the recovery period. In 2/8 high dose animals, the level of inflammation was greater when compared to other animals and was accompanied by anterior chamber flare, fibrin, corneal edema, pupil incomplete dilation, fundus hazy view, corneal vessels and/or lens opacities. These observations correlated with microscopic

findings. At the high dose, these consisted of minimal to marked mixed cell (lymphocytes, macrophages, and rarely, neutrophils) inflammation of the anterior chamber (iridocorneal angle), iris, ciliary body, vitreous body and/or retina. At the mid and low dose, findings were limited to minimal to mild cell inflammation in the ciliary body, vitreous body and/or iris. There were no signs of overt tissue damage due to direct toxicity of the test item and no cellular or humoral immune response to RST-001 was detected at any dose level.

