### **3.6.3 Justification for Human Dose**

The doses and injection volume have been calculated by allometric scaling from pre-clinical animal studies. Vitreous humor volume was the scaling factor across species. In general, scaling of the vitreous volume from mice and dogs to humans is 1:100 and 1:2, respectively.

Two nonclinical toxicology studies were conducted in the dog and mouse. The safe intravitreal doses in the dog ranged from [REDACTED] to [REDACTED] vg/eye. For the mouse, the safe intravitreal doses ranged from [REDACTED] to [REDACTED] vg/eye. Two nonclinical pharmacology studies demonstrated efficacy and safety in the mouse at a dose range of [REDACTED] to [REDACTED] vg/eye in a dose range comparable to the toxicology study. Based on these studies, the expected safe dose range in humans is between [REDACTED] and [REDACTED] vg/eye. The dose range in this study ([REDACTED] to [REDACTED] 1 vg/eye of RST-001) is based on the more conservative exposure in the dog, inclusion of potentially efficacious doses, the ability of the manufacturer to concentrate investigational product, and a safe injection volume of 100  $\mu$ L per eye in humans.

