### **3.15.1.2 Enrollment Phase 2a**

If the DSMC considers the safety and tolerability satisfactory and the enrollment stopping rules have not been met after a minimum assessment of one month (to include Month 1 Visit) from treatment of the final patient in Groups A, B, or C, then the sponsor may elect to start enrollment in the second cohort of patients. In Phase 2a, up to approximately 12 patients may be enrolled and receive RST-001 at the maximum tolerated dose.

- If the DSMC considers the data from Phase 1, in their opinion, to be indicative of a treatment benefit for visual acuity/function, then approximately 6 patients will be enrolled in Phase 2a and follow the same eligibility criteria as Phase 1.
- If the DSMC considers the data from Phase 1, in their opinion, to **not** be indicative of a treatment benefit, then approximately 12 patients will be enrolled in Phase 2a.
  - 6 patients must have VA of no-better-than hand motion in the study eye.
  - 6 patients must have VA in the study eye to range from no-worse-than count fingers to 20/200 vision.

A schematic providing an overview of the treatment schedule is illustrated in [Figure 1](#), and the dose-escalation cohorts are illustrated in [Table 1](#) below.

**Figure 1** Overview of the Treatment Schedule**Table 1** Dose Escalation

Phase	Group	Number of patients a	Intravitreal Injection	
			Vector concentration	Volume (µL)
1	A	3	LOW	100
	B	3	MID	100
	C	3	HIGH	100
2a		6-12 b	Choice of dose c from groups A, B, or C	100

a Up to approximately 21 patients will be enrolled in this study.b Number of patients is dependent upon whether or not the DSMC determines that, in their opinion, a treatment benefit for visual acuity/function has been observed in Phase 1.c The maximum tolerated dose.

After completion of the 2-year core study visits, each patient will be enrolled in a long-term follow-up for an additional 3 years to monitor the long-term safety of RST-001.

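### The one-month minimum permits every Phase 1 dosing decision with no scheduled eye examination on or after day 35 at the dose just tested, the earliest time at which the protocol reports inflammation in dogs

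*Protocol*

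**What the plan says.** Protocol 3.15.1.1 sets three of the four holds. Before the rest of a group is treated, safety "will be assessed in the first patient for a minimum of one month (to include Month 1 Visit"). Escalation from A to B may follow "after a minimum assessment of one month (to include Month 1 Visit) from the last treatment group, then approximately 3 patients in Group B", and the step from B to C is worded the same way. Protocol 3.15.1.2 sets the fourth: Phase 2a may open "after a minimum assessment of one month (to include Month 1 Visit) from treatment of the final patient in Groups A, B, or C". In each case the DSMC must be satisfied and the stopping rules must not have been met.

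Table 2 gives Months 1 and 3 a window of 7 days either side, and the SAP (15.2) puts their targets at days 30 and 91. Section 5 lists no visit between them. Section 5.2.15 calls for a complete ophthalmic examination at every post-treatment visit, but Section 5 also allows post-baseline visits to be virtual during the pandemic with the sponsor's agreement.

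On the dog study, 3.6.2.1 states: "RST-001-related findings, consisting of ocular inflammation, were observed beginning at least 5 weeks after administration with an increasing incidence and severity with dose". Anterior uveitis signs "were observed at Week 5 in 8/8 high dose eyes and 3/8 or 1/8 eyes for the mid and low doses, respectively". It adds: "Animals were sacrificed on Day 36 and Day 99". Section 3.6.3 says the human dose range "is based on the more conservative exposure in the dog", among other considerations, and 3.13 warns: "It is not possible for RST-001 to be removed from the eye after injection".

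**The concern.** The protocol reports one timing signal for ocular inflammation, and the shortest permitted hold ends before it. The dog signs included anterior chamber cells and keratic precipitates, which are slit-lamp findings. A symptom report or a virtual visit cannot be relied on to show them. The holds name a visit, not an examination.

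If inflammation in patients followed the dog timing, the next patients could receive an irremovable product before anyone at that dose had been examined on schedule at the relevant time. The step from Group C to Phase 2a matters most. The dog findings were strongest at the high dose, and up to about 12 patients may then be enrolled in parallel (Protocol 4.3). If no benefit is identified in Phase 1, six of them will have count-fingers to 20/200 vision and so more sight to lose.

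**Working it through.** The protocol gives no calculation behind the one-month interval, so there is no figure to reproduce. The check is calendar arithmetic, counted in days after injection.

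**Inputs.** Month 1 target day 30 and Month 3 target day 91 (SAP 15.2); windows of ±7 days for both and Day 7 ±1 (Table 2); a one-month hold taken as 30 days; first dog finding at 5 weeks or later (Protocol 3.6.2.1).

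**1. Visit windows.** Month 1: 30 − 7 = 23 to 30 + 7 = 37, which is 15 possible days. Month 3: 91 − 7 = 84 to 91 + 7 = 98.

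**2. Decision at the minimum.** A decision on day 30 needs the Month 1 visit by then, so the examination falls on day 23-30 (8 possible days). Five weeks is 5 × 7 = day 35. The examination is therefore 35 − 30 = 5 to 35 − 23 = 12 days early.

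**3. The other reading of Week 5.** If it means days 29-35, examinations on days 29-30 (2 of 8) fall inside it. Days 23-28 (6 of 8) are still too early.

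**4. Fastest permitted path.**

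| Group | First patient dosed | Others dosed | Group decision |
|---|---|---|---|
| A | 0 | 30 | 60 |
| B | 60 | 90 | 120 |
| C | 120 | 150 | 180 |

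At each group decision the first patient is at day 60 and the others at day 30. The first patient's Month 3 visit is 84 − 60 = 24 to 98 − 60 = 38 days away; the others' is 84 − 30 = 54 to 98 − 30 = 68 days away. Month 1 is therefore the last scheduled examination for everyone at that dose. Taking a month as 28 or 31 days puts the first patient at day 56 or 62, still before day 84.

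**5. What the dog dates show.** Each dose group had 8 dogs: 2 per sex at each of two sacrifice times, so 4 were sacrificed on Day 36. A Week 5 denominator of 8 means that all were examined before that sacrifice. Day 35 is thus a detection date. No earlier examination results are given, so onset may have been earlier.

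**6. Effect of a 35-day hold.** Six holds take 6 × 35 = 210 to 6 × 37 = 222 days, against 6 × 30 = 180. The addition is 30 to 42 days (30/180 = 17% to 42/180 = 23%). Only 3 of the 15 Month 1 window days (35-37) meet it. If Month 1 is used, the gap from the Day 7 visit (day 6-8) changes from 23 − 8 = 15 to 37 − 6 = 31 days now, to 35 − 8 = 27 to 31 days.

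**The case against.** One month is a floor. The DSMC must find safety satisfactory and may wait, and its review schedule is in a charter not available here. Section 7.4 can suspend enrollment at any time, investigators may add visits (6.2), and 6.1.1.2 already cites the dog finding as a reason for close monitoring with reporting to the DSMC. The virtual-visit allowance is confined to the pandemic and needs sponsor agreement. The mouse toxicology study found no ophthalmic effects through Week 4 and concluded that there were no dose-related effects. Low and mid dose microscopic findings in dogs were minimal to mild, and 4.4 says no dose-limiting toxicity was seen at the highest dose. All of this stands and limits the weight of the point. None of it requires an examination at week 5 before the next patients are treated.

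A reader might infer that toxicity will be missed. The documents do not support that: these safeguards may catch a case, the dog detection date may be later than true onset, and its transfer to patients is assumed.

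A reader might also apply the dog Week 5 rates to three patients: 1 − (7/8)³ = 33% at low, 1 − (5/8)³ = 76% at mid and 100% at high for at least one case. With exact 95% limits on the rates, the ranges are 1-89%, 23-99% and 95-100%. These are at most illustrative upper limits for detecting any inflammation. They match dog and human doses by label only, since the amounts are redacted. The gain over an examination on day 23-30 could be zero. They also say nothing about a changed decision, because escalation stops for a related Grade 3 or higher event, including severe or persistent inflammation. One examination cannot show persistence.

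The most practical objection is that moving Month 1 later gives up an earlier look, when onset may itself be earlier. That is a real cost and is carried into the change proposed.

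**Conclusion.** The point holds as a weakness in the stated minimum. On the fastest permitted path, none of the patients at the dose just tested needs a scheduled examination on or after day 35 before the next decision. That is true of all six decisions and does not depend on whether a month is 28, 30 or 31 days. Under the more lenient reading of Week 5, 6 of the 8 possible examination days are still too early.

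The relevance to patients rests on two assumptions: that dog timing is informative for humans, and that the dog and human doses are comparable. The documents establish neither, though the protocol uses the dog study to set its dose range and to justify its monitoring. The change is worth making because it is cheap and the product cannot be removed. Confidence is medium. The documents do not state enrollment status, so the change helps only decisions still open.

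**What to change.** At the three places in 3.15.1.1 and the one in 3.15.1.2, replace the one-month minimum with: *a minimum of 35 days, to include an in-person complete ophthalmic examination on or after day 35 in every patient treated at the dose just tested*. For first-patient release, that is the first patient. Align the DSMC charter. Naming every patient matters: a rule tied to the last-treated patient would leave others dependent on a visit window that can be missed or met virtually.

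The requirement can be met in two ways. Holding Month 1 on days 35-37 adds no visit, stays inside the current window, and leaves the SAP Month 1 window unchanged (study days 36-38 under its plus-one rule, within 13-47). Any later in-person examination also counts. A site could therefore keep Month 1 near day 30 and add an examination, at the price of an extra visit.

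The cost is about 5-7 days per decision when Month 1 is used. In that case a scheduled examination between Day 7 and day 35 is also given up, and the shortest Day 7 to Month 1 gap rises from 15 to 27 days while the longest stays at 31. The change covers the Week 5 signal only, not persistence or later progression.

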### **3.15.1.2 Enrollment Phase 2a**

If the DSMC considers the safety and tolerability satisfactory and the enrollment stopping rules have not been met after a minimum assessment of one month (to include Month 1 Visit) from treatment of the final patient in Groups A, B, or C, then the sponsor may elect to start enrollment in the second cohort of patients. In Phase 2a, up to approximately 12 patients may be enrolled and receive RST-001 at the maximum tolerated dose.

- If the DSMC considers the data from Phase 1, in their opinion, to be indicative of a treatment benefit for visual acuity/function, then approximately 6 patients will be enrolled in Phase 2a and follow the same eligibility criteria as Phase 1.
- If the DSMC considers the data from Phase 1, in their opinion, to **not** be indicative of a treatment benefit, then approximately 12 patients will be enrolled in Phase 2a.
  - 6 patients must have VA of no-better-than hand motion in the study eye.
  - 6 patients must have VA in the study eye to range from no-worse-than count fingers to 20/200 vision.

A schematic providing an overview of the treatment schedule is illustrated in [Figure 1](#), and the dose-escalation cohorts are illustrated in [Table 1](#) below.

**Figure 1** Overview of the Treatment Schedule**Table 1** Dose Escalation

Phase	Group	Number of patients a	Intravitreal Injection	
			Vector concentration	Volume (µL)
1	A	3	LOW	100
	B	3	MID	100
	C	3	HIGH	100
2a		6-12 b	Choice of dose c from groups A, B, or C	100

a Up to approximately 21 patients will be enrolled in this study.b Number of patients is dependent upon whether or not the DSMC determines that, in their opinion, a treatment benefit for visual acuity/function has been observed in Phase 1.c The maximum tolerated dose.

After completion of the 2-year core study visits, each patient will be enrolled in a long-term follow-up for an additional 3 years to monitor the long-term safety of RST-001.

### 3.15.2 Study Population

The study population consists of patients with advanced RP [REDACTED]  
[REDACTED]

[REDACTED] This patient group is considered to be a suitable population to assess safety and tolerability in this Phase 1 study. Furthermore, the presence of [REDACTED] [REDACTED] will give a valuable opportunity to evaluate efficacy.

Up to approximately 21 patients will be enrolled in this study.

### **3.15.3 Eligibility Criteria**

#### **3.15.3.1 Inclusion Criteria**

[figure not shown]
The following are requirements for entry in the study:

##### **General Inclusion Criteria:**

1. Male or female patients,  $\geq 18$  years of age at time of informed consent
2. Patient has provided written informed consent and written Authorization for Use and Release of Health and Research Study Information have been obtained prior to any study related procedures
3. Patient has the ability to understand and willingness to follow study instructions and is likely to complete all required visits and procedures
4. Women of childbearing potential must have a negative pregnancy test at Screening and at Baseline, and agree to use an effective form of contraception, or be surgically sterile or post menopausal (defined as last menstrual period greater than two years prior to Baseline). Acceptable methods of contraception include hormonal contraception (i.e., birth control pills, injected hormones, dermal patch or vaginal ring), intrauterine device, barrier methods (diaphragm, condom) with spermicide, or surgical sterilization (tubal ligation)
5. Males must use two forms of contraception (including one barrier method for three months following study treatment administration if their partner is of child-bearing potential), or must be surgically sterile

**Ocular Inclusion Criteria:*****Phase 1 and Phase 2a***

1. Diagnosis of advanced RP defined as:

***Phase 1***

3. VA in the study eye of no-better-than hand motion

***Phase 2a***

4. If a treatment benefit is identified by the DSMC:
  - a. VA eligibility criteria will match that of Phase 1.
5. If a treatment benefit is **not** identified by the DSMC:
  - a. VA eligibility criteria will match that of Phase 1 for half of the enrolled patients.
  - b. VA criteria for the other half of the enrolled patients must range from no-worse-than count fingers to 20/200 vision in the study eye.

**3.15.3.2 Exclusion Criteria**

Patients will **not** be excluded if the molecular diagnosis underlying their RP is not known or if there is presence of macular edema due to advanced RP.

However, any one of the following will exclude patients from being enrolled into the study:

**General Exclusion Criteria:**

1. Participation in any investigational drug or device study within six months prior to Day 0;
2. Complicating systemic diseases or clinically significant abnormal baseline laboratory values. Complicating systemic diseases include those in which the disease itself, or the treatment for the disease, can alter ocular function. Examples are malignancies whose treatment could affect central nervous system function (i.e., radiation treatment of the orbit; leukemia with CNS/optic nerve involvement). For the procedure on establishing clinically significant abnormal baseline laboratory values, see Section [5.1.2](#).

3. Immunocompromising diseases, such as hepatitis B, C and HIV, or use of immunosuppressive medications
4. Females who are pregnant, nursing, planning a pregnancy during the study or who are of childbearing potential not using a reliable method of contraception during their participation in the study
5. History or current evidence of hypersensitivity to any component of the study treatment, medications, or diagnostic agents used in the study
6. Immunogenicity assays show presence of neutralizing antibodies to AAV2 above 1:1000 of dilution
7. Use of anti-platelets and anti-coagulants that may alter clotting within 28 days prior to study treatment administration
8. Any other condition that would not allow the potential patient to complete follow-up examinations during the course of the study and, in the opinion of the investigator, makes the prospective patient unsuitable for the study

